5.2 Secondary outcomes

We will also conduct similar GEE models as the one described above to assess if the intervention improves our secondary outcomes of willingness to dispense naloxone, naloxone counseling self-efficacy, and quality of naloxone counseling.

5.3 Sample size and power

Pharmacies in this grocery store chain dispense naloxone once for every 250 opioid prescriptions, on average. With 60 pharmacists, 30 per treatment arm, we have at least 80% power at the 0.05 significance level to detect an increase in naloxone dispensing to 1 for every 100 opioid prescriptions dispensed, assuming a standard deviation of 0.008 (2 in 250 or 0.8 in 100) and depending on the intraclass (within pharmacy) correlation. In other words, we expect the intervention to increase the naloxone dispensing rate from 1 in 250 (0.4%) to 1 in 100 (1%), an increase of 0.6%. So, the sample size is based on a mean difference of 0.6%.

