1. STUDY OBJECTIVES

We are conducting a RCT to evaluate whether Nalox-Comm training increases how often rural pharmacists dispense naloxone compared to completing a more basic online naloxone training that includes minimal communication content. We hypothesize that pharmacists who complete Nalox-Comm will dispense more naloxone in the three months post-intervention (primary outcome) and will report greater willingness to dispense naloxone, higher naloxone counseling self-efficacy, as well as demonstrate higher quality communication about naloxone (secondary outcomes).

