2.2 Randomization and Allocation to Treatment Groups

All 62 rural pharmacies were matched based on their county's opioid prescribing rate and level of rurality (33% or greater). The county opioid prescribing rate for each pharmacy was identified using the Centers for Disease Control and Prevention's opioid prescribing rates²⁰.

Pharmacies were first ordered by opioid prescribing rate (primary matching variable) and then level of rurality. Pharmacies with exact matches were paired first and then the rest of the pairs were matched using the closest value. Using computer-generated random numbers, one pharmacy in each matched pair was randomized to either the control or experimental group.

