2.4 Study Population

The recruitment goal is 60 pharmacists. Each of the 62 pharmacies employs two full-time pharmacists, both of whom can participate. Thus, participants for the RCT (N = 60) will be recruited from a total sample of 124 pharmacists. Eligible pharmacists must meet the following criteria: 1) be age 18 years or older, 2) speak English, 3) work as a full-time pharmacist at one of the participating 62 rural grocery store chain pharmacies. In addition, individuals who are a floater, or non-staff, pharmacist are ineligible.

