4. STUDY EVALUATIONS AND MEASUREMENTS

4.1 Primary outcome

Our primary outcome is change in naloxone dispensing rates measured by comparing pharmacy records of naloxone dispensed in the three months prior to study participation to number of naloxone dispensed in the three months after study completion (Table 2). The grocery store pharmacy chain has agreed to provide us with these naloxone dispensing rates from each of the participating pharmacies at the conclusion of the study. We hypothesize that pharmacies in the experimental group will dispense more naloxone in the three months post-intervention compared to pharmacies in the control group.

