5. STATISTICAL CONSIDERATIONS

Characteristics of pharmacies and pharmacists will be presented by treatment group. Unadjusted statistical comparisons using two sample t-tests and chi-square tests will be made between treatment groups (control vs. intervention group). Generalized estimating equations, (i.e., the GEE method), will be used to analyze the effects of the intervention on the primary and secondary outcome variables, while accounting for the fact that pharmacists are nested within pharmacies.

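### Section 5.3's claim of at least 80% power makes essentially no allowance for clustering: it gives no ICC and no number of contributing pharmacies, and holds only if nearly every participant comes from a different pharmacy

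*Combined protocol and SAP*

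**What the plan says.** Section 5.3 of the combined protocol and SAP states: "With 60 pharmacists, 30 per treatment arm, we have at least 80% power at the 0.05 significance level". The effect is a rise in the naloxone dispensing rate from 0.4% to 1%, "assuming a standard deviation of 0.008 (2 in 250 or 0.8 in 100) and depending on the intraclass (within pharmacy) correlation". It gives no value or range for that correlation, no design effect, and no expected number of contributing pharmacies.

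Other sections bear on what the independent unit is:

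- Section 2.2 randomises pharmacies in matched pairs: "one pharmacy in each matched pair was randomized to either the control or experimental group".
- Section 2.4: "Each of the 62 pharmacies employs two full-time pharmacists, both of whom can participate". The 60 participants come from a pool of 124 pharmacists in 62 pharmacies.
- Section 4.1 has the chain supply "naloxone dispensing rates from each of the participating pharmacies", and its hypothesis is that "pharmacies in the experimental group will dispense more naloxone in the three months post-intervention compared to pharmacies in the control group". Table 2 lists the source as pharmacy records.
- Section 1 words the primary hypothesis in terms of pharmacists.
- Section 5 plans GEE models "while accounting for the fact that pharmacists are nested within pharmacies". Section 5.1 analyses the change from the pre- to the post-intervention quarter, with pharmacist demographics among the covariates.

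**The concern.** A lower bound on power that depends on a quantity the plan leaves open is not a lower bound. With the effect and SD as stated, any positive within-pharmacy correlation among co-workers can only reduce the power.

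The level of the outcome makes this more than a missing parameter. If the chain supplies one rate per pharmacy, two enrolled co-workers share a single outcome value, and the second adds no independent information on the primary outcome.

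The meaning of the SD is also open. Section 5.3 does not say whether 0.008 describes a pharmacist or a pharmacy, or a single-period rate or the pre-to-post change that section 5.1 analyses.

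At stake is how the primary result will be read. A null finding would be judged against 80% power that the design does not secure.

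**Working it through.** **Inputs.** From section 5.3: difference 0.010 − 0.004 = 0.006; SD 0.008; 30 per arm; alpha 0.05. Two-sidedness is my assumption, since the documents do not state it.

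**Step 1: reproduce the stated figure.** Standardised difference d = 0.006/0.008 = 0.75. With n independent units per arm, the noncentrality is d√(n/2). At n = 30 it is 0.75 × √15 = 2.905.

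- Normal: Φ(2.905 − 1.960) = Φ(0.945) = 82.8%.
- Noncentral t, 58 df: 81.5%.

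The claim therefore reproduces when all 60 pharmacists are independent.

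**Step 2: margin.** Normal: n = 2(1.960 + 0.842)²/0.75² = 27.9, so 28 per arm. For the t-test, n = 28.9, so 29 per arm (28 gives 78.7%, 29 gives 80.1%). The largest design effect that 30 per arm can absorb is 30/27.9 = 1.07 (normal) or 30/28.9 = 1.04 (t).

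**Step 3: one value per pharmacy (direct reading of section 4.1).** Sixty pharmacists can come from as few as 60/2 = 30 pharmacies or as many as 60. The pool is 62/2 = 31 per arm. Reaching 29 per arm means 58 pharmacies, so at most two could supply both pharmacists (58 + 2 = 60). By the normal approximation it means 56 pharmacies, with at most four supplying both.

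Power below uses noncentrality 0.75√(n/2) with 2n − 2 df. The detectable difference is the one that gives 80% power at the same n.

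| Pharmacies per arm | Power (t) | Detectable difference at 80% (percentage points) |
|---|---|---|
| 15 | 51% | 0.85 |
| 20 | 64% | 0.73 |
| 23 | 70% | 0.68 |
| 25 | 74% | 0.65 |
| 30 | 81% | 0.59 |

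The table assumes that 0.008 is the SD of the analysed pharmacy-level quantity, a two-sided test, equal arms, the same 0.6-point effect whether one or both pharmacists are trained, no gain from matching or covariates, and no attrition.

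The row for 23 is roughly what enrolment at random would give (an assumption). The chance that neither pharmacist of a pharmacy enrols is (64/124)(63/123) = 0.264, and 62 × (1 − 0.264) = 45.6 pharmacies.

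**Step 4: pharmacist-level records instead.** Suppose such records exist and 0.008 is the pharmacist-level SD. If 30 pharmacies each supply two, the effective n per arm is 30/(1 + ICC). With degrees of freedom from the number of pharmacies (30 − 2 = 28), power is 80.1% at ICC 0, 76% at 0.1, 73% at 0.2 and 63% at 0.5. The ICC at which 80% is lost is about 0.002.

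With 46 pharmacies (32 single, 14 double), the effective n per arm is (32 + 28/(1 + ICC))/2. On 44 df the limit is about 0.06.

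Taking degrees of freedom from the effective sample size instead would put these limits at about 0.04 and 0.09. The choice matters and should be declared.

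**The case against.** The strongest reply is that the sentence already makes the power conditional on the within-pharmacy correlation, and that its arithmetic is correct. Both are true. A reader might infer that the 80% is miscalculated; the documents do not support that, because the figure reproduces for independent units. What stands is narrower: the condition is named but not quantified, and the inputs leave almost no room for it.

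Second, 62 pharmacies and 60 participants allow close to one pharmacist per pharmacy, and then the claim holds. But no rule requires this, and section 2.4 expressly allows both to enrol.

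Third, the hypotheses are directional, and a one-sided 0.05 test would need only 23 per arm (t). No one-sided test is stated, and at 15 per arm it would still give only 64%.

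Fourth, matching, covariates and a change-score analysis could reduce the residual SD and raise power. That is right. As an illustration with no source in the documents, an SD 20% smaller would give 82% at 20 per arm. This is a reason to define the SD, not a defence of the present figure.

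Fifth, section 4.1 points to pharmacy-level data without ruling out pharmacist-level records. This also stands, and the fix allows for it.

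Finally, the trial is called a pilot. It nevertheless tests its primary outcome at 0.05 and makes an explicit power claim.

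**Conclusion.** The concern holds as a power statement that the design does not secure. Assuming a two-sided test, section 5.3 gives 81.5% (t) or 82.8% (normal) for 30 independent units per arm. On the most direct reading of section 4.1, at least 80% is reached only if nearly every participant comes from a different pharmacy. Under the assumptions listed with the table, power could be as low as 51% if every contributing pharmacy enrols both pharmacists.

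A reader might go further and conclude that the trial is underpowered, or that its true power is 51%. The documents do not support that. The number of contributing pharmacies is unknown, and a smaller SD of change would raise every figure. Nor does this point show any fault in type I error or in the effect estimate, since the planned GEE accounts for clustering by pharmacy.

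**What to change.** In section 5.3:

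- Delete *at least*.
- State that the unit of the primary outcome is the pharmacy. If the chain will supply pharmacist-level records, say so here and in section 4.1, and state the assumed ICC.
- State what 0.008 is the SD of (pharmacy or pharmacist; single-period rate or pre-to-post change) and whether the test is two-sided.
- Replace the single power figure with power and detectable difference by number of contributing pharmacies. The tabulated values serve if 0.008 is the SD of the analysed pharmacy-level quantity, and should carry their assumptions as labels. Recompute if the SD is something else.
- If power by ICC is given instead, base the degrees of freedom on the number of pharmacies.

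Then make section 4.1, the opening of section 5 and section 5.1 agree on the unit of the primary outcome, including how pharmacist demographics enter if that unit is the pharmacy.

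The cost is wording and a less favourable stated power unless nearly all participants come from different pharmacies. No extra recruitment or data is needed.

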6. STUDY INTERVENTION

6.1 Control group: Prescribe to Prevent online module

Participants randomized to the control group complete the 55-min online Prescribe to Prevent (P2P) module. P2P consists of videos, didactic content, and quizzes, covering the key naloxone topics listed in Table 1. Two videos included in P2P demonstrate a pharmacist communicating about a potentially fatal opioid drug interaction with: 1) a patient and 2) a provider. Of note, none of the P2P videos demonstrate effective naloxone communication with patients. Pharmacists in the control group can receive 0.125 continuing education units (CEUs) for completing the course.

6.2 Experimental group: Nalox-Comm online module

Pharmacists in the experimental group complete the approximately 30-minute Nalox-Comm online module. The module was developed during Aim 1 of the NIDA-funded study (study #19-0998). Formative data to guide Nalox-Comm content were collected from interviews with 40 pharmacists, 40 patients at-risk of opioid overdose, and 40 caregivers of individuals at-risk of overdose from pharmacies located in rural counties with high rates of opioid-related overdose deaths in Alabama, Iowa, North Carolina, and Wisconsin. Logistical and attitudinal barriers to pharmacists engaging in naloxone counseling with their patients were identified, including: privacy (patients often do not want others to know they take prescription opioids), cost (patients may not be interested in something they cannot afford), safety (patients may be wary about new medications), and stigma (naloxone has some negative associations from news headlines or television shows). Thus, Nalox-Comm includes three separate, approximately 10-min lessons on how to initiate and conduct a conversation about naloxone that addresses these specific communication barriers. Throughout Aim 1 (study #19-0998), a stakeholder development panel of rural community pharmacists advised on module content to ensure relevancy for rural populations.

Nalox-Comm includes multiple video examples of pharmacists conversing with patients about naloxone, in which they demonstrate a stepwise communication approach (C.A.R.E.). C.A.R.E. stands for: show that you Care or have Concern; Ask the patient for permission to counsel them about naloxone; Relate naloxone to patients by explaining their specific risk factors; and Encourage and

Educate patients by making a personal and/or professional recommendation that they get naloxone. Pharmacists in the experimental group can receive 0.10 CEUs for completing the course.

7. SAFETY MANAGEMENT

The primary risk is breach of confidentiality. The study consent form will inform pharmacists that their responses to the surveys and secret shopper observations will not be shared with their employer, results will be reported in aggregate, and will not affect their employment. The online consent will include a check box that states, 'I agree to participate in this research study.' All data will be stored in a secure fashion with password-protected files and secure servers.

We do not anticipate any adverse events (AEs) since the surveys and intervention assess naloxone knowledge, attitudes, and communication/training preferences and scenarios will be realistic and not outside the range of what pharmacists would be asked to navigate as part of their normal professional duties. However, the secret shopper interactions may still cause the pharmacist to feel uncomfortable, and thus potential mild AEs include pharmacist discomfort and possible emotional outburst when engaging in the secret shopper encounter. Secret shoppers will be trained to handle possible negative reactions from the pharmacist, although the likelihood of a negative reaction is low. Due to the nature of our study, we do not anticipate encountering situations in which confidentiality could be breached because of mandatory reporting. However, if the pharmacist reacts negatively to the scenario and it is clear that they need medical assistance or counseling, confidentiality may be breached to ensure the safety of the pharmacist. The consent form will state that confidentiality will be breached in the case that a pharmacist needs medical assistance or counseling.

The study research team members are trained in confidentiality procedures. Identification numbers will be assigned to pharmacists and any information that could identify individuals participating in this project will not be included in any data sets. The data will only be given to the PI and research staff. Data will not be shared with the pharmacists' employers.

8. DATA AND SAFETY MONITORING

The study PI will evaluate data collected by secret shoppers and through surveys. The PI will also meet weekly with her project director and monthly with the research team to discuss data collection, potential data quality issues if they arise, and study progress. These meetings will serve as a forum to discuss issues related to data collection and implementation of the data collection protocol. Meetings will be held more frequently if needed.

Additionally, an independent and unbiased review of the study's ongoing progress will be provided by the DSMB. The DSMB is well-qualified to comment on the appropriateness of the RCT protocol and make recommendations related to any AEs or adjustments to study procedures. The investigator(s) will appoint a DSMB chairperson. S/He is responsible for overseeing the meetings and developing the agenda in consultation with the investigator(s). The DSMB will meet at least once per year and will schedule additional meetings, if deemed necessary. A quorum of more than half the DSMB members is required in order to convene a meeting of the DSMB.

9. CONSENT PROCESS

Informed consent documents for this study include a specific statement that information from the trial will be posted on ClinicalTrials.gov. Consent will be obtained on the online baseline survey. The first page of the baseline survey will contain a study consent form that includes the requirements, risks, and benefits of participation. The consent form will also include a checkbox stating that “I agree to participate in this research study” that pharmacists check to consent to participate in the study. Pharmacists will have the ability to opt out of the study. The consent form will notify pharmacists that secret shoppers will observe their communication over the 3-month study period. The consent form will also state that the secret shopper will not disclose their identity, but the pharmacist will be notified after the study has been completed of when the phone calls occurred. The consent form will also state that data collected during the secret shopper visit will not be shared with their employers. Pharmacists who do not wish to participate in the research study will not be penalized by their employer.

APPENDIX

Figure 1: Study Design

[figure not shown]

Table 1: Summary of the P2P and Nalox-Comm Modules

	Prescribe to Prevent	Nalox-Comm
Length	55 minutes	~30 minutes
Format	Online module with videos, didactic content, quizzes	Online module with videos, didactic content, reflection
Topics covered	
 • Risk factors for overdose • How to respond to overdose • How naloxone works • Types of naloxone • How to administer naloxone • Medico-legal issues • How to stock, fill, and bill for naloxone 	
 • The importance of naloxone and the role of the pharmacist • Non-stigmatizing language • How to initiate an offer of naloxone • How to respond to patient & caregiver naloxone requests • How to address specific communication barriers

Table 2: Study measures

Variable	Source	# of items	Baseline	Immediate post-intervention	Within 4 weeks post-intervention	3-month follow-up
Primary Outcome						
Naloxone dispensing rate	Pharmacy records	-	X			X
Secondary Outcomes						
Willingness to dispense naloxone	Self-report survey	7	X	X		X
Naloxone counseling self-efficacy	Self-report survey	7	X	X		X
Quality of naloxone counseling	Direct observation	6	X		X	
Other Measures						
Naloxone knowledge	Self-report survey	8	X	X		X
Attitudes toward dispensing naloxone	Self-report survey	8	X	X		X
Barriers to dispensing naloxone	Self-report survey	10	X	X		X
Previous naloxone training	Self-report survey	1	X			X
Pharmacist characteristics	Self-report survey	7	X			
Pharmacy characteristics	Self-report survey	3	X			
Social desirability bias	Self-report survey	10	X
